4.1.3. Maintenance Study (Phase 3 Maintenance Study)

The study population for the Phase 3 Maintenance Study will be clinical responders from Induction Study 1 or Induction Study 2. The following populations will be rerandomized in a 1:1:1 ratio to guselkumab 200 mg SC q4w, guselkumab 100 mg SC q8w, or placebo SC:

- Guselkumab clinical responders at Week I-12.
- Placebo crossover responders at Week I-24.

Participants will be allocated to an intervention group using permuted block randomization stratified by clinical remission status at maintenance baseline (Yes/No), concomitant use of corticosteroids at maintenance baseline (Yes/No), and induction treatment (guselkumab 400 mg, guselkumab 200 mg, placebo crossover [guselkumab 200 mg], and placebo crossover [guselkumab 400 mg, if chosen as the Phase 3 guselkumab induction dose]). The primary analysis population of the Maintenance Study will comprise randomized and treated participants who have a modified Mayo score of 5 to 9 at induction baseline. In addition to the aforementioned randomized population, guselkumab 24-Week responders and induction placebo responders at Week I-12 from Induction Study 1 or Induction Study 2 will enter the Maintenance Study but will not be rerandomized.

[figure not shown]
Treatment assignments for these groups are shown in the study schema (Figure 4). Placebo SC q8w will be given to the guselkumab 100 mg SC q8w group starting at Week M-0 to maintain the blind throughout the duration of the Maintenance Study. Further information on study intervention administration for the Maintenance Study is provided in Section 6.1.3.

Participants meeting criteria for loss of clinical response (ie, no longer satisfies the definition of clinical response as previously defined in Section 3) during the Maintenance Study will be eligible for a single blinded dose adjustment as described in Section 6.6.1. For additional details on the management of clinical flare and loss of clinical response see Section 4.1.3.1.

For participants who are receiving oral corticosteroids on entry in the Maintenance Study, the investigator must begin tapering the daily dose of corticosteroids at Week M-0 (Section 6.5.1). Other UC-specific medical therapies (ie, oral 5-ASA compounds, 6-MP, AZA, or MTX) must be maintained at stable doses through Week M-44 unless investigator judgment requires that the therapy be discontinued, or the dose reduced because of toxicity or medical necessity (Section 6.5).

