For testing of the major secondary endpoints, the efficacy of each guselkumab group versus placebo will be compared. For all statistical comparisons of the major secondary endpoints (except for clinical remission at Week M-44 among the participants who had achieved clinical remission at maintenance baseline), a CMH test (2-sided) stratified by clinical remission status at maintenance baseline (Yes/No) and induction dose treatment (guselkumab 400 mg, guselkumab 200 mg, placebo crossover [guselkumab 200 mg], and placebo crossover [guselkumab 400 mg, if chosen as the Phase 3 guselkumab induction dose]) will be used. For clinical remission at Week M-44 among the participants who had achieved clinical remission at maintenance baseline, a CMH test (2-sided) stratified by induction dose treatment (guselkumab 400 mg, guselkumab 200 mg, placebo crossover [guselkumab 200 mg], and placebo crossover [guselkumab 400 mg, if chosen as the Phase 3 guselkumab induction dose]) will be used.

Type I error control for Rest of World (ie, countries/territories outside the United States): A multiple testing procedure will be employed to control the overall Type 1 error rate over the primary and all major secondary efficacy analyses at the 2-sided 0.05 significance level within a

guselkumab dose group. For this procedure, a fixed sequence testing procedure will be used for the primary endpoint, with the higher dose group being tested first. Following this, the major secondary endpoints will be tested in a hierarchical manner for each dose group that is significant for the primary endpoint and the testing order will be specified in the SAP. A major secondary endpoint for a guselkumab dose group will be considered significant only if both the previous endpoints in the hierarchy and current endpoint test positive at the 2-sided 0.05 level of significance. If an endpoint is not significant, all subsequent tests in the hierarchy will be considered not to be significant. Nominal p-values will be reported for all analyses that are not multiplicity controlled.

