1.3. Phase 3 Maintenance Study

In the randomized-withdrawal maintenance study, all participants enrolled will be clinical responders from Induction Study 1 or Induction Study 2. The schema for the maintenance study is shown in Figure 2.

The randomized population of the maintenance study is composed of the following participants:

- Guselkumab clinical responders at Week I-12.
- Placebo crossover responders at Week I-24: Participants initially randomized to placebo who are not in clinical response at Week I-12 who then crossover to guselkumab induction IV treatment and achieve clinical response at Week I-24.

These participants will be randomized in a 1:1:1 ratio to one of three maintenance groups:

- guselkumab 200 mg subcutaneous (SC) q4w
- guselkumab 100 mg SC q8w
- placebo SC

Participants will be allocated to an intervention group using permuted block randomization stratified by the following factors:

• clinical remission status at maintenance baseline (Yes/No) based on the local endoscopy subscore,

- concomitant use of corticosteroids at maintenance baseline (Yes/No), and
- induction treatment (guselkumab 400 mg IV, guselkumab 200 mg IV, placebo crossover to guselkumab 200 mg IV).

[figure not shown]
In addition to the aforementioned randomized population, guselkumab 24-week responders (i.e., participants initially randomized to guselkumab IV in an induction study who are not in clinical response at Week I-12 who then receive 3 doses of guselkumab 200 mg SC and achieve clinical response at Week I-24) and placebo responders at Week I-12 from Induction Study 1 or Induction Study 2 will enter the Maintenance Study but will not be randomized. Induction placebo responders will receive placebo SC, and guselkumab 24-week clinical responders will receive guselkumab 200 mg SC q4w.

To maintain the blind, all participants will receive study intervention at all scheduled study intervention visits i.e., M-0 to M-40 every 4 weeks. Participants who discontinue from study intervention administration in maintenance should have a final safety follow-up visit approximately 12 weeks after their last dose of study intervention.

Participants in the randomized population who subsequently lose response at any scheduled visit between Week M-8 and Week M-32 will be eligible to have a one-time dose adjustment (Section 1.3.1.)

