1.5. Randomization and Blinding

Randomization will be used to minimize bias in the assignment of participants to treatment groups, to increase the likelihood that known and unknown participant attributes (e.g., demographic and baseline characteristics) are evenly balanced across treatment groups, and to enhance the validity of statistical comparisons across treatment groups. Blinded treatment will be used to reduce potential bias during data collection and evaluation of clinical endpoints.

Intervention Allocation

Central randomization will be implemented based on a computer-generated randomization schedule prepared before the study by or under the supervision of the sponsor.

In the Maintenance Study, participants in the randomized population will be randomly assigned to 1 of 3 treatment groups in a 1:1:1 ratio. The randomization will be balanced by using randomly permuted blocks and will be stratified by clinical remission status at maintenance baseline (Yes/No), concomitant use of corticosteroids at maintenance baseline (Yes/No), and induction dose treatment (guselkumab 400 mg, guselkumab 200 mg, placebo crossover to guselkumab 200 mg).

An Interactive Web Response System (IWRS) will assign a unique treatment code, which will dictate the treatment assignment and matching study intervention kit(s) for the participant. The requestor must use his or her own user identification and personal identification number when contacting the IWRS and will then give the relevant participant details to uniquely identify the participant.

Blinding

To maintain the study blind, the study intervention container will have a label containing the study name, study intervention number, and reference number. The study intervention number will be entered in the electronic case report form (eCRF) when the study intervention is dispensed for onsite administration. Each active study intervention and its matching placebo will be identical in appearance.

Data that may potentially unblind the treatment assignment (i.e., study intervention serum concentrations, antibodies to study intervention) will be handled with special care to ensure that the integrity of the blind is maintained and the potential for bias is minimized. This can include making special provisions, such as segregating the data in question from view by the investigators, clinical team, or others as appropriate until the study unblinding.

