5.3.2.1. Analysis Methods

5.3.2.1.1. Main Estimator (Analysis) for the Primary Estimand

The primary endpoint is clinical remission at Week M-44 (as defined in Section 5.3.1. above).

The primary endpoint will be analyzed based on the Primary Estimand, Estimand 1 (Section 5.3.2.). After accounting for the ICE strategies, participants who are missing any or all of the Mayo subscores that comprise the primary endpoint at Week M-44 will be considered not to be in clinical remission at Week M-44 (i.e., nonresponder imputation). For participants experiencing ICE 5, their observed clinical remission status (if available) at Week M-44 will be used.

In the primary analysis, data from all participants in the **Randomized Full Analysis Set** (Section 4) will be analyzed according to the randomized study intervention regardless of the study intervention they actually received.

Summaries of the proportion of participants in clinical remission at Week M-44 (as well as the associated 95% confidence interval) by treatment group, the adjusted treatment difference (with Cochran-Mantel-Haenszel weight) between each guselkumab treatment group and the placebo group, as well as the associated 95% confidence interval will be presented.

For testing of the primary endpoint, the efficacy of each guselkumab group versus placebo will be compared. For all statistical comparisons of the primary endpoint, a Cochran-Mantel-Haenszel (CMH) test (2-sided) stratified by clinical remission status at maintenance baseline (Yes/No), and induction dose treatment (guselkumab 400 mg, guselkumab 200 mg, placebo crossover to guselkumab 200 mg) will be used.

A multiplicity-controlled testing procedure, starting with the high guselkumab dose group (200 mg SC q4w), will be used to control the overall Type-I error rate at the 0.05 level (2-sided) over the primary and major secondary endpoints. The study will be considered positive if the test involving

the high maintenance dose group shows a statistically significant difference versus placebo for the primary endpoint of clinical remission at Week M-44 (see Section 5.4.1.3).

Testing Procedure:

The multiple testing procedure to control the Type 1 error will be different for the United States and the countries outside the United States, as described below.

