5.3.2.2.2. Sensitivity Analyses 2: Multiple Imputation

A multiple imputation method will be utilized to impute missing Mayo score components pertaining to the primary endpoint after the intercurrent event rules have been applied. This method involves the following distinct steps:

- 1. Any missing Mayo components pertaining to the primary endpoint at Week M-44 will be imputed N times (e.g., 200) to generate N complete data sets using the fully conditional specification (FCS) method, assuming missing at random (MAR). The following variables will be included in the imputation model: Mayo components pertaining to the primary endpoint at Week I-0 of an induction study and at Week M-0 and Week M-44 of the maintenance study, induction dose factor, and the maintenance treatment group.
- 2. Each of the N resulting data sets will be analyzed using a logistic regression model with treatment group, induction baseline modified Mayo score, and induction treatment as covariates. The modified Mayo score was used as the baseline disease activity measure as it contains the same Mayo components as those for the definition of clinical remission.
- 3. The results from the N data sets will be combined to produce inferential results.

5.3.2.2.3. Sensitivity Analyses 3: Exclusion of Participants Whose Data Cannot be Source Data Verified Due to Major Disruption

A sensitivity analysis will be performed based on the **Randomized Full Analysis Set** with the exclusion of participants whose data cannot be source data verified prior to the Week M-44 DBL due to major disruption, including COVID-19 and regional crisis in Russia and Ukraine. This analysis will use the same ICE strategies as those for the primary estimand, and missing data handling rule as those for the primary analysis. Data for participants that cannot be source data verified will be documented prior to the Week M-44 DBL and study unblinding.

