5.4.1.3. Main Estimators (Analyses) for the Secondary Estimands

The major secondary endpoint analyses will be based on the **Randomized Full Analysis Set**. For all statistical comparisons of the major secondary endpoints (except for clinical remission at Week M-44 among the participants who had achieved clinical remission at maintenance baseline), a CMH test (2-sided) stratified by clinical remission status at maintenance baseline (Yes/No) and induction dose treatment (guselkumab 400 mg, guselkumab 200 mg, placebo crossover to guselkumab 200 mg) will be used. In cases of rare events, Fisher's exact test will be used for treatment comparisons.

For clinical remission at Week M-44 among the participants who had achieved clinical remission at maintenance baseline, a CMH test (2-sided) stratified by induction dose treatment (guselkumab 400 mg, guselkumab 200 mg, placebo crossover to guselkumab 200 mg) will be used.

Summaries of the proportion of participants achieving each major secondary endpoint by treatment group as well as the associated 95% confidence interval, the adjusted treatment difference (with Cochran-Mantel-Haenszel weight) between each guselkumab treatment group and the placebo group, as well as the associated 95% confidence interval will be presented.

Missing Data Rules for the Secondary Estimands:

After accounting for the ICE strategies, any missing data for the major secondary endpoints will be handled with nonresponder imputation. In particular, the following rules will be used:

[figure not shown]
- Participants who are missing any or all of the 3 Mayo subscores that comprise the modified Mayo score will be considered not to have achieved corticosteroid-free clinical remission, maintenance of clinical response, or maintenance of clinical remission.
- Participants who have a missing endoscopy subscore at Week M-44 will be considered not to have achieved endoscopic healing or histologic-endoscopic mucosal healing or endoscopic normalization at Week M-44.
- Participants who are missing any or all of the components in the Geboes grading system pertaining to histologic healing endpoint will be considered not to have achieved histologic-endoscopic mucosal healing.
- Participants who are missing either stool frequency or rectal bleeding subscores at Week M-44 will be considered not to have achieved symptomatic remission at Week M-44.

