To account for the missing data (after applying the ICE strategies) for continuous endpoints of change from baseline measured at more than one post-baseline visit through Week M-44, a Mixed-Effect Model Repeated Measures (MMRM) will be used, under the assumption of missing at random (MAR), to test the difference between each guselkumab group and placebo. In MMRM, missing data will not be imputed, but rather missing data will be accounted for through correlation of repeated measures in the model. Additionally, if the MMRM normality assumption is in question, an appropriate transformation may be implemented before fitting the MMRM model.

The explanatory variables of the MMRM model will include treatment group, clinical remission status at maintenance baseline (Yes/No), and induction dose treatment (guselkumab 400 mg, guselkumab 200 mg, placebo crossover to guselkumab 200 mg), respective baseline score, and an interaction term of visit with treatment group.

An unstructured covariance matrix for repeated measures within a participant will be used. The F-test will use Kenward-Roger's approximation for degree of freedom. In case of lack of convergence, empirical structured covariances will be used in the following order until convergence is reached: 1) Toeplitz 2) first order Autoregressive Moving Average.

The treatment difference between each guselkumab group and placebo will be estimated by the difference in the least squares means (LSmeans). The 95% 2-sided CI for the differences in LSmeans and p-values will be calculated based on the MMRM.

Endpoints that are measured at only one post-baseline visit through Week M-44 (e.g., the full Mayo score or modified Mayo score) will be compared between each guselkumab group and placebo using an analysis of covariance (ANCOVA) with treatment group, clinical remission status at maintenance baseline (Yes/No), induction dose treatment, and corresponding baseline value as covariates.

For analyses using ANCOVA, unless otherwise specified, multiple imputation (same as defined in Section 5.3.2.2.2.) will be used for missing data (after applying ICE strategies), under the assumption that the data are missing at random. The analysis will impute the missing scores at Week M-44 using the corresponding value at baseline and related component score at pre-Week M-44 visits if applicable, clinical remission status at maintenance baseline, induction dose treatment, and treatment group.

Ordinal Endpoints

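### Corticosteroid use at maintenance baseline stratifies the randomization but is dropped from the CMH strata; restoring it is a small gain at almost no cost

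*SAP*

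**What the plan says.** SAP 1.3 and 1.5 and Protocol 4.1.3 and 6.3 stratify the maintenance randomization by three factors. Besides remission status at maintenance baseline, SAP 1.5 lists "concomitant use of corticosteroids at maintenance baseline (Yes/No), and induction dose treatment".

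The analysis uses two of them. SAP 5.3.2.1.1 specifies "a Cochran-Mantel-Haenszel (CMH) test (2-sided) stratified by clinical remission status at maintenance baseline (Yes/No), and induction dose treatment" for the primary endpoint, and the CMH-weighted difference is reported alongside it. SAP 5.4.1.3 repeats this for the major secondary endpoints, with "a CMH test (2-sided) stratified by clinical remission status at maintenance baseline (Yes/No) and induction dose treatment". The exception is maintenance of remission among baseline remitters, which is stratified by induction treatment alone. Protocol 9.4.2.3.2 and 9.4.2.3.3 match.

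The other models do not bring the factor back:
- Sensitivity analysis 2 (SAP 5.3.2.2.2) uses a "logistic regression model with treatment group, induction baseline modified Mayo score, and induction treatment as covariates".
- SAP 5.5.3 states: "The explanatory variables of the MMRM model will include treatment group, clinical remission status at maintenance baseline (Yes/No), and induction dose treatment", plus the baseline score and a visit-by-treatment term. The ANCOVA and log-rank analyses in that section also omit corticosteroid use.

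The induction studies differ. Their CMH tests (Protocol 9.4.2.1.2 and 9.4.2.2.2) do stratify by baseline corticosteroid use.

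**The concern.** Stratified randomization balances corticosteroid use between arms, so that factor adds almost no variance to the treatment difference. A CMH variance computed without it does not know this. It still counts the spread between users and non-users as noise. The test then rejects less often than 5% under the null, and the interval is wider than it needs to be.

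This matters only if corticosteroid use at M-0 predicts outcome within the remission-by-induction strata. That is plausible here. Tapering is mandatory from M-0 (Protocol 6.5.1). Several of the medication changes that count as failure are defined against the maintenance-baseline corticosteroid dose (SAP Attachment 2). Corticosteroid-free remission is itself a major secondary endpoint. At stake is a little power, mainly for the endpoints the plan powers least: maintenance of remission (74%) and endoscopic normalization (65%). Both sit in hierarchies where one failure ends confirmatory testing of everything after it.

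**Working it through.** **The plan's own figures.** Inputs from SAP section 3: 25% vs 45%, two-sided 0.05, 90% power. With the pooled-variance formula:

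n = [1.96·√(2·0.35·0.65) + 1.2816·√(0.25·0.75 + 0.45·0.55)]² / 0.20² = (1.322 + 0.845)² / 0.04 = 117.4, so 118 per group, as stated.

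Power at 161 per group is 96.7% (stated 97%). All five rows of SAP Table 1 also reproduce.

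**Inputs for the check**
- From the documents: 484 participants, 1:1:1; 33% in remission at M-0; M-44 remission of 36% vs 61% in those participants.
- Derived rates in the rest: placebo (0.25 − 0.33·0.36)/0.67 = 19.6%; guselkumab (0.45 − 0.33·0.61)/0.67 = 37.1%.
- Derived induction mix: about 78 / 279 / 127 (400 mg, 200 mg, placebo crossover). The first two assume 60% response and 200 mg in Induction Study 2; the 127 is in SAP Table 2.
- Assumed, because the documents are silent: share on corticosteroids q (20-50%); a rate d points lower in users within strata, equal in both arms (0 to 20); block size 6.

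**Analytic approximation.** Within-stratum variance at the placebo rates:

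V = 0.33·0.36·0.64 + 0.67·0.196·0.804 = 0.1815.

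The share of it due to corticosteroid use is f = q(1−q)d²/V. The planned interval is too wide by the factor k = 1/√(1−f), and the true size is 2[1 − Φ(1.96k)]. At q = 40%:
- d = 10 points: f = 0.0024/0.1815 = 0.0132; k = 1.0067; size 4.85%.
- d = 20 points: f = 0.0096/0.1815 = 0.0529; k = 1.0275; size 4.4%.

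**Simulation.** 200,000 trials per scenario, permuted blocks within 12 cells, CMH without continuity correction, 200 mg q4w vs placebo, q = 40%:

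| Gap d | Size, planned → factor added | Mean 95% CI width at 25% vs 45% (points) | Power, clinical remission |
|---|---|---|---|
| 0 | 4.9% → 4.9% | 19.89 → 19.90 | 97.3% → 97.3% |
| 5 | 5.0% → 5.0% | 19.89 → 19.87 | 97.3% → 97.3% |
| 10 | 4.8% → 4.9% | 19.88 → 19.78 | 97.4% → 97.4% |
| 20 | 4.4% → 5.0% | 19.88 → 19.43 | 97.6% → 97.9% |

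Other runs with 30-50% on corticosteroids put the planned size at 4.3-4.6% for d = 20. Coverage at d = 20 and q = 40% is 95.4% → 94.9%.

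**Power gain by endpoint** (percentage points, range over runs with 30-50% on corticosteroids):

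| Endpoint | d = 10 | d = 20 |
|---|---|---|
| Clinical remission | 0.05-0.07 | 0.2-0.3 |
| Corticosteroid-free remission | 0.1-0.16 | 0.6-0.8 |
| Maintenance of remission (159 participants, 3 vs 6 strata) | 0.17-0.36 | 1.1-1.45 |
| Endoscopic normalization (no remission effect assumed) | 0.4-0.5 | 1.7-2.3 |

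With no gap, adding the factor costs at most 0.08 points.

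**Sparse strata.** Cells rise from 6 to 12. The smallest (400 mg, in remission, on corticosteroids) holds about 322 × 78/485 × 0.33 × 0.4 = 7 participants over the two arms compared. Some stratum was empty in one arm in 0.2-3.4% of simulated trials, with no measurable loss of power.

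**The case against.** The planned test is valid, pre-specified and the same in both documents. Stated power is met without the change: 97.3-97.6% simulated against 97% for clinical remission, and 91.4-92.0% against 90% for corticosteroid-free remission. All of that stands.

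The larger gains come from a strong assumption. At q = 40%, a 20-point gap among placebo non-remitters means 7.6% in users against 27.6% in non-users, an odds ratio of about 4.6. For endoscopic normalization it means 6% against 26%, about 5.5. The 20-point column is therefore an upper case. At 10 points the primary endpoint gains almost nothing.

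The plan does not ignore the factor. SAP 5.3.2.1.2 calls for subgroups by the maintenance stratification factors, and SAP 5.5 analyses several endpoints among participants on corticosteroids at maintenance baseline. Neither adjusts the main test.

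The induction CMH tests also drop a randomization factor, region, so using fewer strata may be a preference. Those same tests keep corticosteroid use, though, which leaves its omission here unexplained.

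Finally, participants with a modified Mayo score of 4 are randomized and then excluded from the primary population. This loosens the exact balance slightly, so the conservatism may be a little smaller than simulated.

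**Conclusion.** The concern holds as a small, conditional efficiency loss. It is neither an error nor a conflict between the documents. If corticosteroid use at M-0 is at most weakly prognostic within strata (5 points or less), there is no visible effect. At 10 to 20 points, with 30-50% on corticosteroids, the planned test runs at about 4.8% down to 4.3-4.6% instead of 5%. Its intervals are about 0.3-0.7% too wide at 10 points and 1.7-2.8% at 20. The gain for the primary endpoint is at most about 0.3 points of power; for the two weakest secondary endpoints it reaches 1 to 2 points in the strong case. Prevalence, effect size and block size are assumptions. Because the downside is close to nil, the change should be made.

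**What to change.** Before the Week M-44 unblinding:
- Add corticosteroid use at maintenance baseline (Yes/No, as randomized in IWRS) to the CMH strata and weights for the primary and all major secondary endpoints, including maintenance of remission.
- Pre-specify that a stratum with no participants in one arm is pooled over induction treatment. Judging this over all three arms together keeps the strata the same for both dose comparisons.
- In the same edit, align the remaining models so that no new inconsistency arises: the multiple-imputation logistic model (SAP 5.3.2.2.2), the supplementary estimands (5.3.2.3.1), and the CMH, MMRM, ANCOVA and log-rank analyses in 5.5.3.
- Amend Protocol 1.1, 9.4.2.3.2 and 9.4.2.3.3, or record the change in SAP Appendix 2, which now reports no changes to protocol-planned analyses.

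If the team prefers two factors, it should state why. After unblinding, the three-factor analysis could only be a labelled sensitivity analysis.

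The cost is document and programming work. No participants, visits or data are needed, since the factor is already captured at randomization.
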